9.7.3 Methods to control/assess confounding

Crude and adjusted measures of association will be computed comparing the exposed vs the unexposed (prevalence ratios, risk ratios, mortality rate ratios). Adjustment will be performed by the covariates measured, with LMP as the anchor date. Covariates will be included in the

appropriate regression model: log-binomial regression for prevalences and risks and Cox proportional-hazards regression for incidence rate ratios. Candidate covariates for inclusion in the analyses will vary by database. A propensity-score based adjustment may be considered and will be described in a separate Statistical Analysis Plan. Table 5 shows country-specific availability of the covariates.

Table 5 Proposed candidate covariates and data availability in participating databases

Variable/data type	AVAILABILITY OF DATA IN THE DATABASE (either via diagnosis code or procedure or treatment proxy)				
	DENMARK (NATIONAL REGISTRIES)	ITALY/ARS TOSCANA	NORWAY (NATIONAL REGISTRIES)	SPAIN/SIDIAP	UK/CPRD
Pregnancy feasibility counts for interim reports	Hospital-based ICD-10 codes for pregnancy related diagnoses or codes for prenatal visits from the Insurance registry for primary care prenatal visits	Hospital-based ICD-10 codes for pregnancy related diagnoses or codes for prenatal visits from the Insurance registry for primary care prenatal visits	All pregnancies in Norway that last at least 12 weeks are captured in the Medical Birth Registry of Norway (mandatory notification to the registry, 100% coverage)	Most pregnancies will be identifiable in primary care; some might be missed without linkage to hospital data	Pregnancy information will be available in the main primary care dataset following primary care and/or secondary care contact with the patient. This will be based on Read and/or SNOMED codes.
Country of residence	YES	YES	YES	YES	YES
Calendar year of delivery	YES	YES	YES	YES	YES
Pregnant woman's age	YES	YES	YES	YES	YES
Marital or cohabiting status	YES	To be verified	YES	To be verified	YES
Smoking	YES	To be verified	YES	YES	YES
Alcohol use (also ICD codes)	YES, IF BASED ON ICD CODES	YES	YES, IF BASED ON ICD CODES	To be verified	YES

Confidential

Post-marketing safety study for COVID-19 mRNA-1273 vaccine

Protocol mRNA-1273-P905, Date: 27 September 2021, Version 1.2

Marital status or other available socioeconomic measures	YES	YES	YES	YES Other available socioeconomic measures	YES
Gravidity	YES	YES	YES	YES	YES
Parity	YES	YES	YES	YES	YES
Placenta previa	YES	YES	YES	YES	YES
Caesarean delivery	YES	YES	YES	YES	YES
Multifetal pregnancy	YES	YES	YES	YES	YES
Prior (before participating pregnancy) still birth	YES	YES	YES	To be verified	YES
Prior (before participating pregnancy) child SGA	YES	YES	YES	YES	YES
Prior (before participating pregnancy) pregnancy with preeclampsia	YES	YES	YES	To be verified	YES
Cardiovascular diseases (eg hypertension, migraine)	YES	YES	YES	YES	YES
Respiratory diseases (eg asthma COPD)	YES	YES	YES	YES	YES
Type 2 diabetes	YES	YES	YES	YES	YES
Gestational diabetes	YES	YES	YES	YES	YES
Cancer	YES	YES	YES	YES	YES
Mental-health disorders	YES	YES	YES	YES	YES
Rheumatic diseases	YES	YES	YES	YES	YES
Systemic lupus erythematosus	YES	YES	YES	YES	YES
Inflammatory bowel disease	YES	YES	YES	YES	YES
Multiple sclerosis	YES	YES	YES	YES	YES
Type 1 diabetes	YES	YES	YES	YES	YES

Outpatient prescriptions/dispensings	YES	YES	YES	YES	NO
BMI or obesity	YES	YES	YES	YES	YES
History of COVID-19 infection	YES	YES	YES	YES	YES
HCRU measures (mother)	YES	YES	YES	YES	YES

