9.3.3 Covariates

The key covariates will include country of residence, calendar year of delivery, pregnant woman's age, smoking, alcohol use (whenever measured), marital status or other available socioeconomic measures, gravidity, parity, placenta previa, caesarean delivery, multifetal pregnancies, prior reproductive history (prior still birth, prior child SGA, prior pregnancy with preeclampsia) selected chronic comorbidities (cardiovascular diseases, respiratory diseases, type 2 and gestational diabetes, cancer, mental-health disorders, and autoimmune diseases [rheumatic diseases, systemic lupus erythematosus, inflammatory bowel disease, multiple sclerosis, type 1 diabetes, thyroid disorders, medication use]), selected medication use, body mass index (BMI), and history of COVID-19 infection

Specific covariates' availability may vary by database and will be described in the SAP.

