9.6. Data management

This study, which will be conducted based on this common protocol, will use the Vaccine monitoring Collaboration for Europe (VAC4EU, <https://vac4eu.org/>) research environment based on a common protocol, and a common data model (CDM).¹⁶ The work will be conducted using a distributed network of the participating data access providers (DAPs), all of whom have experience and have contributed to the CONSIGN project. The work will proceed according to Model C (Figure 1): each DAP will extract the data required for the study and transform their local patient level data into a CDM. It is proposed to use the ConcePTION CDM, which is publicly available¹⁶ and is being specifically developed for multinational studies of medication safety in pregnancy. Extraction, transformation, and loading (ETL) design and instructions are available, as well as tools to check the quality of the data for the AESI estimated utilized for the ACCESS

background rate protocol. A common program to run quality checks, data transformation, and analysis will be prepared, verified and distributed to all DAPs. Aggregate results and summary estimates resulting from the programs will be returned to the coordinating center for pooled meta-analysis and reporting. The full approach will be developed and described in the Statistical Analysis Plan (SAP).

[figure not shown]

Figure 1. Options for multi-database studies in Europe¹⁷

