9.7.5 Sensitivity analyses

The following sensitivity analyses of the primary outcomes will be conducted:

- Using the date of pregnancy start as (LMP – 30 days) as an alternative definition to correct for imprecisions in LMP determination
- Alternative comparators may be explored, including contemporaneous other vaccinations (eg. influenza) or pregnancies vaccinated before LMP
- Repeating the analysis to examine the association between receipt of Spikevax in the 2nd or 3rd (but not 1st) trimester and a given major congenital malformation outcome. This is a negative control exposure analysis because exposure beyond 1st trimester cannot plausibly cause malformations, and any observed association will be due to bias.¹⁸
- Different definitions of SGA will be examined:
 - o birth weight below 2 standard deviations from sex- and gestational-week specific mean birth weight (a more specific definition, with expected prevalence of SGA of about 1%);
 - o birth weight below 10th percentile of sex- and gestational-week specific mean birth weight (more sensitive definition, with expected prevalence of SGA of about 10%)

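### Log-binomial is the only regression named for adjusted prevalence and risk ratios; for preterm birth, and for SGA near 10% prevalence with strong predictors, it can often fail to give a valid standard error

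*Protocol*

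**What the plan says.** Section 9.7.3 states that covariates enter the "appropriate regression model: log-binomial regression for prevalences and risks", with Cox regression for the rate outcome. It adds: "Adjustment will be performed by the covariates measured, with LMP as the anchor date". No other regression is named for prevalence or risk ratios, and nothing is said about non-convergence.

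The covariate set is not final. Section 9.7.3 says "Candidate covariates for inclusion in the analyses will vary by database", and Table 5 lists about 30 candidates. The same paragraph leaves a second route open: "A propensity-score based adjustment may be considered and will be described in a separate Statistical Analysis Plan".

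Section 9.3.3 counts "placenta previa, caesarean delivery, multifetal pregnancies, prior reproductive history" among the key covariates. Table 5 marks "Multifetal pregnancy" as available in all five databases. Section 9.2.1 makes all pregnancies eligible, Table 4 analyses preterm birth and SGA in live births, and section 9.7.1 takes the newborn as the unit for neonatal outcomes. Twins are therefore in the analysis and count separately.

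Section 9.6 says: "A common program to run quality checks, data transformation, and analysis will be prepared, verified and distributed to all DAPs". Aggregate results go to the coordinating centre, and section 9.7.6 recommends random-effects models if they are pooled.

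**The concern.** A log-binomial model multiplies a baseline risk by one ratio per covariate, and every fitted risk must stay at or below 1. When several strong predictors meet in one birth, the likelihood is maximised on that limit. Iteratively reweighted least squares (IRLS) then often does not converge, and the usual standard error does not apply.

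Adjusted ratios for preterm birth and SGA belong to the primary outcomes. Each source has to return an estimate with a valid standard error for pooling. The coordinating centre receives only aggregates and cannot refit, and section 12 says that only one data extraction is feasible. A failure found when the program runs would have to be handled by a rule chosen after the data are seen.

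**Working it through.** **The plan's own figure.** Table 3 follows from U = exp[(1.96 + z) × √((1 − p)/(n₁p) × (1 + 1/k))]. For SGA with n₁ = 16,667, k = 5 and p = 0.1, the root is √(0.9/1,666.7 × 1.2) = 0.02546.

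- 80% probability (z = 0.8416): exp(2.8016 × 0.02546) = 1.07, as stated.
- 90% probability (z = 1.2816): exp(3.2416 × 0.02546) = 1.09, as stated.

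All 24 rows reproduce to within about 0.006. The formula is for an unadjusted ratio, so Table 3 does not show whether the adjusted model can be fitted. The protocol gives no figure for that.

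**Mechanism.** A fitted risk reaches 1 when the product of the remaining ratios equals 1 divided by the risk already reached.

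- Preterm birth, assumed multifetal risk 40%: 1/0.40 = 2.5. One or two further strong predictors are enough.
- SGA at 10%, assumed multifetal ratio 2: 1/(0.10 × 2) = 5.
- SGA at 1%, same ratio: 1/(0.01 × 2) = 50.
- Neonatal death, assumed 0.3%: 1/0.003 = 333.

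**Inputs.** From the protocol: 20,000 and 100,000 births, and 9.1% exposed (9,091 of 100,000), from Table 3; the SGA definition described as "more sensitive definition, with expected prevalence of SGA of about 10" per cent, and the other at about 1%, from section 9.7.5. Assumed, because the protocol does not give them: preterm prevalence (6% in simulation B), covariate frequencies and all covariate effects.

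**Simulation A** (10 covariates, logistic truth, no vaccine effect, multifetal preterm risk about 37–43%; 150–200 runs at 20,000 births, 25–40 at 100,000). A run failed if IRLS with step-halving stuck, hit its iteration limit or ended on the boundary.

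- Preterm birth: 23% (weak other effects) to 84% (moderate) failed at 20,000, and 32% to 100% at 100,000.
- SGA at 10%: 55% failed. Neonatal death: under 1%.
- Poisson with robust variance gave an estimate in every 10-covariate preterm and SGA run, with test size 4–5%.

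**Simulation B** (about 30 candidate-type covariates, logistic truth, 20,000 births, 10 runs per cell). The likelihood was maximised with fitted risks held below 1, and IRLS was run separately. Cells show runs on the boundary, then runs in which IRLS converged.

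| Preterm birth, covariates used | Multifetal ratio 3 | Ratio 5 | Ratio 8 |
|---|---|---|---|
| Full list | 3; 6 | 5; 4 | 10; 0 |
| LMP-anchored only | 1; 10 | 3; 8 | 9; 1 |
| LMP-anchored, other effects weakened | 0; 10 | 3; 10 | 6; 7 |

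The LMP-anchored rows leave out placenta previa, caesarean delivery and gestational diabetes, which a strict reading of the anchor excludes.

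- Preterm birth at 100,000 with ratio 8: boundary in every run (only 3–4 runs per setting).
- Singletons only: 0–2 of 10 at 20,000 and 0–1 of 4 at 100,000.
- SGA at 10%, strong effects: 6–10 of 10 at 20,000 and 4 of 4 at 100,000. Weakened effects: 0 of 10 and 0 of 3.
- SGA at 5%: 0–1 of 10 at 20,000. SGA at 2%: 0 of 10 at 20,000 and at most 1 of 4 at 100,000.
- Log-binomial on exposure plus propensity-score quintiles: interior solution in 20 of 20 runs.
- Poisson returned an exposure ratio in every run. The constrained log-binomial ratio differed from it by 0.01–0.27 standard errors on average, at most 0.64.

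**Simulation C** (11 terms, preterm birth, assumed multifetal odds ratio 10). Log-binomial converged in 15 of 30 runs at 20,000 and 1 of 8 at 100,000; Poisson converged in all. With weak covariate effects, failures were 0–1 runs.

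**The case against.** The strongest reply is that this is SAP territory. Table 5 lists candidates with their availability, not a model. No functional form is given for age or BMI, and the final covariate set and the handling of non-convergence are ordinary SAP content. The propensity-score route is open in the same paragraph and showed no boundary problem. Log-binomial is also a standard estimator of the stated measure.

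Much of this stands. A reader might infer that the protocol fixes a model with 20 or more covariates; it does not. A reader might also infer that affected sources would have no usable ratio. That is not shown: a constrained estimate exists and lies close to Poisson. What is lost is mainly a valid standard error, and whether the fit stops depends on the software. Nor do the documents say that sites would drop covariates locally; section 9.6 describes one verified common program.

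What does not stand is that nothing has been decided. Section 9.7.3 states the regression method, while the propensity score only may be considered. An SAP written to the protocol inherits log-binomial, for outcomes and covariates where it is fragile.

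**Conclusion.** The point holds in limited form. For preterm birth, and for SGA at about 10% prevalence with strong predictors, a multivariable log-binomial fit can often end on the boundary, leaving no converged fit or no valid standard error. For preterm birth the frequency runs from about 0% with weak effects to most runs with a strong multifetal effect. With strong effects it is higher at 100,000 births than at 20,000, so the largest sources are the most exposed.

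These frequencies rest on assumed prevalences and effects, and simulation B and the larger sizes used few runs; they show a range and do not forecast a rate. It would be wrong to extend the point to every prevalence or risk outcome: neonatal death, SGA at 5% or below and singleton-only analyses are little affected, and low birth weight was not simulated. It is a weakness in a stated method that should be corrected before the common program is distributed.

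**What to change.** In section 9.7.3, name Poisson regression with a log link and robust variance, clustered by mother, as the model for adjusted prevalence and risk ratios in the common program. At the least, make it the pre-specified fallback, with the same trigger in all sources. Clustering is needed because the newborn is the unit for neonatal outcomes and siblings from one pregnancy are not independent. A propensity-score adjustment with few terms would also serve, if the SAP adopts it as the stated method.

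The cost is about one sentence in the protocol and a small change to the program. The target remains the prevalence or risk ratio, with a negligible loss of efficiency. Poisson can give fitted risks above 1: in the strong-effect settings of simulation B at 100,000 births, about 9 to 41 births per run on average. It also does not cure very rare covariates with no events, which had no finite coefficient in some 21-covariate and neonatal-death runs. These need one common rule for merging or dropping.

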9.7.4 Subgroup analyses

All relevant analyses will be stratified by country, maternal age, sex, calendar time, trimester and seasonality if applicable and in subgroups specified in Section 9.3.4 where sample size permits.

9.7.5 Sensitivity analyses

The following sensitivity analyses of the primary outcomes will be conducted:

- Using the date of pregnancy start as (LMP – 30 days) as an alternative definition to correct for imprecisions in LMP determination
- Alternative comparators may be explored, including contemporaneous other vaccinations (eg. influenza) or pregnancies vaccinated before LMP
- Repeating the analysis to examine the association between receipt of Spikevax in the 2nd or 3rd (but not 1st) trimester and a given major congenital malformation outcome. This is a negative control exposure analysis because exposure beyond 1st trimester cannot plausibly cause malformations, and any observed association will be due to bias.¹⁸
- Different definitions of SGA will be examined:
 - o birth weight below 2 standard deviations from sex- and gestational-week specific mean birth weight (a more specific definition, with expected prevalence of SGA of about 1%);
 - o birth weight below 10th percentile of sex- and gestational-week specific mean birth weight (more sensitive definition, with expected prevalence of SGA of about 10%)

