9.2.3 Study Period

In the prevalence study, there is no follow-up per se, as study population will be assembled based on existing (prevalent) outcomes.

In the cohort study, for the outcome of neonatal death, the maximum follow-up will be 28 days postnatally, censored at emigration or end of data. For the outcome pregnancy-related death, the maximum follow-up will be 1 year after pregnancy end,¹² censored by emigration or end of data availability.

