9.3. Variables

9.3.1 Exposure

The exposure will be defined by a record of receipt of at least one dose of Spikevax during pregnancy.

For the purposes of timing of exposure, trimesters of pregnancy will be defined as follows:

- First trimester: from the first day of the last menstrual period (LMP) to LMP+97 days (both dates inclusive);
- Second trimester: from LMP+98 days to earliest of (LMP+202 days, pregnancy end) (both dates inclusive);
- Third trimester: from LMP+203 days (inclusive) until pregnancy end date (not included)

Pregnancies unexposed to Spikevax vaccine will be categorized as unexposed or as exposed to other COVID-19 vaccines and other non-COVID-19 vaccines (influenza, meningococcal disease, pneumococcal disease, rubella, shingles, tuberculosis), overall and trimester-wise. Pregnancies among women who received Spikevax before LMP will be enumerated and may be used as an additional comparator, group size permitting.

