9.7.1 Descriptive analyses

Counts and percentages will be presented for categorical variables (age at conception in categories, sex). Means, standard errors, medians and ranges will be presented for continuous variables (age at conception). The proportion of missing data will be described when appropriate. For maternal outcomes, pregnancy will be the unit of observation; for neonatal outcomes, a newborn will be the unit of observation. For the outcomes of congenital malformations and stillbirth the number at risk will be the total number of live or stillborn children.

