9.7.2 Measures of occurrence and measures of association

Prevalence of each outcome will be computed as number of observations with a given outcome divided by the total number of study population members. For neonatal death, a 28-day mortality risk will be the measure of occurrence among live-born infants. Prevalence/risks will be compared according to predefined exposure categories and using, whenever necessary,

plausible exposure risk windows. For example, for assessing the outcome of congenital malformations, births will be classified based on their exposure in the first trimester. For all other neonatal outcomes, exposure any time in pregnancy and per trimester may be considered.

Table 4 summarizes outcome-specific analysis populations and exposure windows.

Table 4 Summary of outcome-specific analysis populations and relevant exposure windows

Outcome	Analysis population	Relevant exposure window
Hypertensive disorders of pregnancy (preeclampsia, eclampsia, gestational hypertension)	All pregnancies	1st or 2nd trimester
Gestational diabetes	All pregnancies	1st or 2nd trimester
Bleeding during pregnancy	All pregnancies	1st or 2nd trimester
Postpartum haemorrhage	All pregnancies	Any time during pregnancy
Pregnancy-related death	All pregnancies	Any time during pregnancy
Fetal death (spontaneous abortion or stillbirth)	A combined population of stillbirths, livebirths, and pregnancies ending in a spontaneous abortion	Any time during pregnancy
Termination of pregnancy for fetal anomaly (TOPFA)	All pregnancies	Any time during pregnancy
Any elective pregnancy termination	All pregnancies	Any time during pregnancy
Ectopic pregnancy	All pregnancies	Any time during pregnancy
Fetal growth restriction/small for gestational age (SGA)	Live births	Any time during gestation
Preterm birth (<37 full gestational weeks)	Live births	Any time during gestation
Low birth weight (<2500 g)	Live births	Any time during gestation
Major congenital malformations	Live or stillbirths/TOPFA (whenever available) without evidence of teratogenic exposure or infection or chromosomal anomaly	First trimester
Microcephaly (based on head circumference)	Live births without evidence of teratogenic exposure or infection or chromosomal anomaly	Any time during gestation
Low 5-minute Apgar score	Live births	Any time during gestation
Neonatal death (death within 28 days of birth)	Live births	Any time during gestation

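### Where terminations for fetal anomaly are counted, the late-dose negative control for malformations is pulled below 1 by their shortened exposure window, a bias the first-trimester analysis largely lacks

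*Protocol*

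**What the plan says.** The negative control is listed in Protocol section 9.7.5: "Repeating the analysis to examine the association between receipt of Spikevax in the 2nd or 3rd (but not 1st) trimester", with a malformation as the outcome. The stated reason is that "exposure beyond 1st trimester cannot plausibly cause malformations, and any observed association will be due to bias". No analysis population is given for it.

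Table 4 (section 9.7.2) sets the population for major congenital malformations as "Live or stillbirths/TOPFA (whenever available) without evidence of teratogenic exposure or infection or chromosomal anomaly", with first-trimester exposure as the relevant window. Section 9.7.1 gives a different one: "For the outcomes of congenital malformations and stillbirth the number at risk will be the total number of live or stillborn children". The data-analysis part of the abstract (section 4) agrees with 9.7.1.

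Under section 9.3.1 the first trimester runs to LMP+97. The second opens at LMP+98 and closes at LMP+202 or at pregnancy end, whichever is earlier. The third opens at LMP+203. The measure is a prevalence ratio (section 9.1.1), and section 9.2.3 adds: "In the prevalence study, there is no follow-up per se, as study population will be assembled based on existing (prevalent) outcomes".

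**The concern.** A negative control exposure helps if it carries the same bias as the main analysis and adds none of its own. Here the two analyses differ in a way that matters once TOPFA are in the population. A TOPFA after day 97 has lived through its whole first trimester and could have been exposed like any other pregnancy in the main analysis. In the control, its exposure window is cut short at termination, or never opens, while nearly all non-cases keep the full window to birth. In a prevalence design nothing accounts for the lost window. Cases therefore gather in the unexposed group and the ratio falls below 1.

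Two things are at stake. If morbidity-related confounding raises the malformation ratio, the downward shift can offset it and the control sits near 1. If there is no confounding, the control falls below 1 and shows a bias that the main estimate largely does not have. Because TOPFA are included only where a source records them, the shift also varies across sources and can look like heterogeneity.

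**Working it through.** **The plan's own figure.** The protocol gives no figure for the control. Table 3, any major malformation, 16,667 exposed, 5 comparators per exposed, prevalence 0.05, is reproduced by exp[(1.96 + z) × √((1−p)/(n₁p) × (1 + 1/5))]. This gives 1.109 with z = 0.8416 and 1.127 with z = 1.2816, against 1.11 and 1.13 stated. The same standard error gives a 95% interval factor around a ratio of 1 of exp(1.96 × √(0.95/833.35 × 1.2)) = 1.08.

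**Inputs from the protocol.** Malformation prevalence m = 0.05 (Table 3); window opening at day 98 (9.3.1); coverage q = 1/6, the 5:1 row of Table 3, used here for second- and third-trimester doses.

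**Assumptions, because the protocol gives no values.** Constant dosing rate from day 98; births at day 280; every TOPFA in the population is a case; TOPFA share of cases s = 5 to 30%; TOPFA at day g, with 140 (20 weeks) as the central value and 90 to 168 as the range. No effect and no confounding.

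**Exposure probability.** For a birth it is q = 0.167. For a TOPFA at day g > 98 it is 1 − (1−q)^((g−98)/182), and zero before that. At g = 140 the open share of the window is 42/182 = 23%, giving 1 − (5/6)^0.2308 = 0.041. The open share is 8% at 16 weeks and 38% at 24 weeks.

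**Worked case, s = 20%, g = 140.**
- Exposed cases: 0.05 × (0.2 × 0.0412 + 0.8 × 0.1667) = 0.00708
- Unexposed cases: 0.05 − 0.00708 = 0.04292
- Exposed non-cases: 0.95 × 0.1667 = 0.15833
- Unexposed non-cases: 0.95 × 0.8333 = 0.79167
- Prevalence in exposed: 0.00708/0.16541 = 0.0428
- Prevalence in unexposed: 0.04292/0.83459 = 0.0514
- Ratio: 0.83

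**All shares, coverage 1/6, no effect and no confounding.** In the last column, coverage of 1/6 is total uptake from LMP to day 280, and the comparator is women with no dose in pregnancy.

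| TOPFA share of cases | Control, TOPFA at 20 weeks | Control, TOPFA at day 90 to 168 | First-trimester analysis, TOPFA at 20 weeks |
|---|---|---|---|
| 5% | 0.96 | 0.94–0.97 | 0.995 |
| 10% | 0.92 | 0.89–0.93 | 0.99 |
| 20% | 0.83 | 0.78–0.87 | 0.98 |
| 30% | 0.75 | 0.67–0.80 | 0.97 |

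If the first-trimester comparator is instead all women without a first-trimester dose, that column is 1.00 throughout. Over coverages from 1/21 to 0.50, the control ranges from 0.56 to 0.97. In live and still births only, with equal gestation, the control is 1.00.

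**Offsetting.** Multiply the odds of exposure among cases by 1.2. The births-only control reads 1.19; with a 20% TOPFA share at 20 weeks it reads 0.99. With a multiplier of 1.1, 1.09 in births becomes 1.00 at a 10% share.

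**The case against.** The strongest reply is that the protocol does not settle on a TOPFA-inclusive control. Section 9.7.1 and the abstract count live and stillborn children only. On that text the control is already births-only and this mechanism disappears. Table 4 adds TOPFA only where available, and section 9.3.2.1 leaves outcome-specific windows and population restrictions to a statistical analysis plan that is not shown. This stands as a limit: the bias exists only where Table 4 is followed and TOPFA are recorded. It does not clear the plan, because Table 4 is the protocol's outcome-by-outcome statement of populations and the two passages cannot both hold.

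A reader might infer more than the text supports, in four ways:
- That TOPFA pregnancies cannot be exposed in the control window. This is so only before LMP+98; later ones have a shortened window, and the protocol gives no timing.
- That the control falls below 1 in every data source. It does not where TOPFA are absent.
- That section 9.9 predicts upward confounding of malformations. It says confounding in either direction cannot be ruled out, and states upward bias conditionally and for some outcomes.
- That the protocol would clear the main result on a control near 1, or discount it on a control below 1. No such rule is written. Taken literally, the sentence attributing any association to bias survives, since a shortened window is a bias. The trouble is that the main analysis largely lacks it.

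The size is also not anchored. At a 5% share the pull is 3 to 6% at coverage 1/6, inside the interval factor of 1.08.

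**Conclusion.** The point holds in this limited form. Where TOPFA are included, the negative control carries a downward bias of its own that the first-trimester estimate largely lacks. The direction follows from the protocol's windows and Table 4, given that non-cases mostly run to birth. The size rests on an assumed TOPFA share, TOPFA timing, coverage and constant dosing rate: about 0.96 to 0.75 for shares of 5 to 30% at 20 weeks and coverage 1/6. At a share of 10% or more the shift is about as large as the interval half-width with 16,667 exposed, and it can offset confounding of similar size. The contradiction between Table 4 and sections 9.7.1 and 4 needs no assumption. The documents do not show that the control fails everywhere or that a biased main result would be accepted. This should be corrected before analysis.

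**What to change.** 1. Reconcile Table 4 with section 9.7.1 and the abstract on whether TOPFA belong in the malformation population.
2. In section 9.7.5, state that the negative control is run in live and still births only, for exposed and comparator alike.
3. Show the first-trimester estimate in the same births-only population beside it. A TOPFA-inclusive first-trimester estimate can still be reported.
4. Limit the stated reading to bias that the control shares with that births-only first-trimester estimate.

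It may be tempting also to disregard doses given after a prenatal diagnosis of an anomaly. This should not be done: only cases have such a date, so it cuts exposure in cases alone. The algebra is the one above. With diagnosis at 20 weeks in 10, 20 or 30% of malformed births, the births-only control falls to 0.92, 0.83 or 0.75.

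The cost is one population filter, one extra column of results and slightly fewer cases in the control. A smaller shift could remain if malformed births end earlier than others.
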